3.7.2 Dose Limiting Toxicities (DLTs)

The Dose-Limiting Toxicities in this study are defined in Section 3.1.1.1 in the protocol.

All DLTs will be listed based on the DLT Evaluable Set.

3.7.3 Clinical Laboratory Tests

Clinical laboratory evaluations will be summarized using descriptive statistics for selected laboratory parameters (i.e., chemistry and hematology) including absolute measurements and changes from baseline for the minimum post-baseline value, maximum post-baseline value, and last post-baseline value. Selected clinical laboratory tests including Alanine Aminotransferase (ALT), Aspartate Aminotransferase (AST), total bilirubin (TBIL), creatinine, hemoglobin, absolute neutrophil count (ANC), and platelets. Both scheduled and unscheduled post-baseline visits will be considered for the summaries of the last, maximum, and minimum post-baseline values. All clinical laboratory analytes are listed in Appendix A.

Abnormal laboratory results will be graded according to NCI-CTCAE version 5.0 as applicable. For some laboratory tests, the CTCAE criteria may include qualifying definitions (e.g., clinical AE and/or requirement for concomitant medication) in addition to the specific laboratory value used

for the definition of the toxicity grades. For such tests, the qualifying definitions will not be used for the assignment of toxicity grades.

A shift table, presenting the 2-way frequency tabulation for baseline and the worst post treatment value according to the NCI-CTCAE grade will be provided for selected clinical laboratory tests including Alanine Aminotransferase (ALT), Aspartate Aminotransferase (AST), total bilirubin (TBIL), creatinine, hemoglobin, absolute neutrophil count (ANC), and platelets. Both scheduled and unscheduled post-treatment visits will be considered in tabulation of the worst post-treatment value.

For purposes of analysis and reporting, laboratory values will be standardized using International System of Units (SI) or clinically appropriate units.

The number and percentage of patients with treatment-emergent laboratory abnormalities (any grade and grade ≥3 per NCI-CTCAE v5.0) will be presented for applicable hematology and serum chemistry laboratory parameters. Treatment-emergent laboratory abnormalities are defined as post baseline laboratory abnormalities with worsening CTCAE grade from baseline. Post-baseline laboratory abnormality with unknown baseline grade will be considered as treatment-emergent.

The number and percentage of patients with the following potentially clinically significant abnormal liver function tests at any post-Baseline visits will be summarized:

- ALT ≥3xULN, ≥5xULN, ≥10xULN, and ≥20xULN
- AST ≥3xULN, ≥5xULN, ≥10xULN, and ≥20xULN
- Total bilirubin ≥2xULN
- Potential Hy's Law cases: ALT or AST ≥3×ULN with total bilirubin ≥2×ULN and ALP <
 2xULN at the same visit date

Laboratory values that are reported using a nonnumeric qualifier (e.g., less than [<] or greater than [>] sign), the reported numeric value will be used for analysis without the qualifier.

Clinical laboratory evaluations for selected parameters (i.e. chemistry and hematology) will be listed by patient, tabulated by study arm, and abnormal values will be flagged.

3.7.4 Vital Signs

Vital signs will be measured in the supine position after at least a 10-minute rest at screening, Visit 1 of each dosing cycle, the end of treatment (EoT) Visit, and the Safety Follow-up Visit. At dosing visits, vital signs will be assessed before dosing (after ECG assessment) and at 15 minutes (±5 minutes), 30 minutes (±5 minutes), and 1 hour (±10 minutes) after dosing. The following variables will be measured:

- Systolic and diastolic blood pressure (mm/Hg);
- Pulse rate (beats per minute); and
- Temperature (°C).

Changes from baseline to the last, maximum, and minimum post-baseline values will be presented. Both scheduled and unscheduled post-treatment values will be considered for summaries of the last, minimum, and maximum.

The number and proportion of patients with potentially clinically significant changes in vital signs will be presented based on the following thresholds:

- Systolic blood pressure ≥ 160 mmHg and increase ≥ 20 mmHg from baseline,
- Diastolic blood pressure ≥ 100 mmHg and increase ≥ 15 mmHg from baseline, and
- Pulse rate ≥ 120 bpm with increase ≥ 15 bpm from baseline.

All vital signs data will be listed by patient and tabulated by study arm.

3.7.5 Electrocardiograms

The Electrocardiogram parameters PR interval, RR interval (RR), QRS Duration (QRS), QT interval (QT), Bazett-corrected QT interval (QTcB), and Fridericia-corrected QT interval (QTcF) will be summarized using descriptive statistics for actual values and for changes from baseline by scheduled time of evaluation, including the last post-baseline and the maximum post-treatment value. Both scheduled and unscheduled post-treatment values will be considered for summaries of the last and maximum post-treatment values.

The Bazett-corrected QT interval (QTcB) is based on the following formula:

$$QTcB (msec) = \frac{QT (msec)}{\sqrt[2]{RR}(msec)/1000}$$

The Fridericia-corrected QT interval (QTcF) is based on the following formula:

$$QTcF (msec) = \frac{QT (msec)}{\sqrt[3]{RR}(msec)/1000}$$

In addition, the number and percentage of patients experiencing QTcF or QTcB elevation at any time post-baseline will be presented for the following categories:

- QTcF > 450 ms,
- QTcF > 480 ms,
- QTcF > 500 ms.
- Increase from baseline QTcF > 30 ms.
- Increase from baseline QTcF > 60 ms,
- QTcB > 450 ms,
- QTcB > 480 ms,
- QTcB > 500 ms.
- Increase from baseline QTcB > 30 ms, and
- Increase from baseline QTcB > 60 ms.

All ECG measurements and overall interpretation will be listed by patient and tabulated by study arm.

3.7.6 Physical Examinations

All physical examination data will be listed by patient.

3.7.7 Performance Status

All ECOG performance status data will be listed by patient.

4 DATA MONITORING COMMITTEE

The monitoring of the safety and tolerability of CyPep-1 + pembrolizumab will be performed by the DMC.

This will include all the patients in the Phase 1b portion and thereafter, all patients who have entered the study. This will be conducted on a regular basis, as defined in the DMC charter.

After the DMC reviews the safety data, feedback will be provided to the Sponsor regarding the further conduct of the study. The DMC will be comprised of independent members or designees. The DMC will strive for a consensus opinion regarding the data reviewed.

5 ANALYSIS TIMING

5.1 Interim Analysis

[figure not shown]
No formal interim analysis is planned.

5.2 Pre-Final Analysis

After the database is locked the pre-final analysis will be generated. Pre-final tables, figures and listings (TFLs) will be provided approximately 3 weeks after database lock.

5.3 Final Analysis

After all comments on the pre-final analysis have been resolved and the study database is declared final, the final analysis will be generated. Final TFLs will be provided approximately 1 week after the study database is declared final. If there were no changes to the pre-final analysis or the study database, the pre-final TFLs may be considered final.

7 PROGRAMMING SPECIFICATIONS

Analyses will be performed using SAS® version 9.4 or higher. All available data will be presented in patient data listings which will be sorted by patient and visit date as applicable.

will

be followed for the validation of all SAS programs and outputs.

Detailed Programming Specifications will be provided in a separate document.

APPENDIX A: CLINICAL LABORATORY ANALYTES

Standard Safety Chemistry Panel

Alanine aminotransferase Albumin
Alkaline phosphatase Amylase
Aspartate aminotransferase Bicarbonate

Blood urea nitrogen/urea C-reactive protein

Calcium Chloride
Creatine kinase Creatinine

Estimated glomerular filtration rate Gamma-glutamyl transferase

Glucose Lactate dehydrogenase

Lipase Phosphate
Potassium Sodium

Total bilirubin Total protein

Uric acid

Hematology

Absolute neutrophil count Hematocrit Hemoglobin Platelets

Red blood cell count White blood cell count and differential [1]

1. Including neutrophils, eosinophils, basophils, lymphocytes, and monocytes. Manual microscopic review is performed only if white blood cell count and/or differential values are out of reference range.

Coagulation

Activated partial thromboplastin time International normalized ratio [1]

Prothrombin time

1. In case there are no normal ranges available for the prothrombin time, the international normalized ratio may be used instead of prothrombin time.

Urinalysis

Bilirubin pH

Creatinine Specific gravity

Ketones Blood
Microscopy [1] Glucose

Leukocyte esterase Protein

Nitrite Urobilinogen

1. Microscopy is performed only as needed based on positive dipstick test results.

Pregnancy Test [1]

Serum human chorionic gonadotropin

Urine human chorionic gonadotropin

1. For female patients of childbearing potential only.

Endocrinology

Follicle-stimulating hormone [1] Free thyroxine

Thyroid-stimulating hormone Triiodothyronine [2]

1. Follicle-stimulating hormone will only be performed in female patients who have spontaneous amenorrhea for at least 2 years to verify their post-menopausal status.

2. Or free triiodothyronine.

Serology

Human immunodeficiency virus

APPENDIX B: RESPONSE EVALUATION CRITERIA IN SOLID TUMORS (RECIST) VERSION 1.1 (V1.1)

Measurable TumorBurden	A maximum of 5 target lesions in total (and up to 2 per organ) can be identified atbaseline and measured through the course of therapy.	
Minimum Size of Measurable	≥10 mm in longest diameter (LD) and 2× the slice thickness for extranodal lesions.	
Lesions	≥15 mm in short axis diameter (SAD) for nodal lesions.	
	≥10 mm in LD for clinical lesions (must be measured using electronic calipers).	
	≥20 mm in LD for chest X-ray (if clearly defined and surrounded by aerated lung);CT is preferable.	
	Ultrasound cannot be used to measure lesions.	
Lymph Nodes	Lymph nodes are considered pathologically enlarged if >10 mm in SAD. To be	
	measurable, nodal lesions must be ≥15 mm in SAD.	
	Nodal lesions with SAD >10 mm and <15 mm are nonmeasurable.	
	The sum of the diameters (LD for extranodal target lesions, SAD for nodal lesions)is followed through the course of therapy.	

l .		
Bone Lesions	A lytic or mixed lytic-blastic bone lesion with a soft tissue component assessed on CT/MRI can be measurable if the minimum size criteria are met.	
	Blastic bone lesions and bone lesions assessed on bone scan, positron emissiontherapy (PET), or plain films are nonmeasurable.	
Cystic Lesions	Lesions that meet the criteria for radiographically defined simple cysts are not malignant. Cystic lesions thought to be metastases can be measurable if they meetthe minimum size criteria. Noncystic lesions are preferable.	
Lesions With PriorLocal Treatment	Lesions in previously irradiated areas (or areas treated with local therapy) are notmeasurable unless the lesion has progressed since therapy.	
Too Small to Measure	If a target lesion becomes too small to measure, a default value of 5 mm is assigned. If the lesion disappears, the measurement is recorded as 0 mm.	
Lesions That Split orCoalesce	If extranodal target lesions fragment, the LDs of the fragmented portions are added to calculate the sum. If target lesions coalesce and cannot be distinguished, the LDof the coalesced lesion is added to the sum.	
Definition of CompleteResponse (CR)	CR requires the disappearance of all extranodal lesions, the regression of all nodallesions to <10 mm SAD, and the normalization of tumor marker level.	
Definition of PD	PD is assessed if the sum of the diameters has increased by ≥20% and ≥5 mm fromnadir (including baseline if it is the smallest sum).	
	Patients with measurable disease: for "unequivocal progression" based on nontarget disease, there must be an overall level of substantial worsening that merits discontinuation of therapy (if target disease is SD/PR).	
	Patients without measurable disease: for "unequivocal progression" of nontarget disease, the increase in overall tumor burden must be comparable to the increaserequired for PD of measurable disease.	
Assessment of NewLesions	New lesions should be unequivocal and not attributable to differences in scanning technique or findings, which may not be a tumor (ie, "new" bone lesions may be healing or flare of preexisting lesions). If it is equivocal, repeat scans are needed toconfirm. If confirmed, PD is assessed at the date of the initial scan. Lesions identified in anatomic locations not scanned at baseline are considered new. New lesions on US should be confirmed on CT/MRI.	
FDG-PET	New lesions can be assessed using FDG-PET: (-) PET at baseline and (+) PET at follow-up is PD based on a new lesion. No PET at baseline and (+) PET at follow-upis PD if the new lesion is confirmed on CT. If a subsequent CT confirms the new lesion, the date of the PD is the date of the initial PET scan. No PET at baseline and (+) PET at follow-up corresponding to preexisting lesion on CT that is notprogressing; not PD.	
Recurrence of Lesions	For a patient with SD/PR, a lesion that disappears and then reappears will continue to be measured and added to the sum. Response will depend on the status of the other lesions. For a patient with CR, reappearance of a lesion would be considered PD.	

Overall Response	One overall response table integrates target, nontarget, and new lesions and anothertable integrates nontarget and new lesions for the assessment of patients without measurable disease.
Confirmation ofResponse	Confirmation of PR/CR is ONLY required for nonrandomized studies where response is the primary endpoint. In these studies, subsequent confirmation of PR with 1 interim timepoint of SD is acceptable.

APPENDIX C: DESCRIPTION OF THE IRECIST PROCESS FOR ASSESSMENT OF DISEASE PROGRESSION

Immune-Response Evaluation Criteria in Solid Tumors (iRECIST) is based on the Response Evaluation Criteria in Solid Tumors (RECIST) version (v)1.1 but adapted to account for the unique tumor response seen with immunotherapeutic drugs. iRECIST will be used by the Investigator to assess tumor response and progression and to guide decisions about changes in management.

Assessment at Screening and Prior to the RECIST v1.1 Progression

Until radiographic disease progression based on modified RECIST v1.1, there is no distinct iRECIST assessment.

Assessment and Decision at the RECIST v1.1 Progression

For patients who show radiological progressive disease (PD) by RECIST v1.1, the Investigator will decide whether to continue a patient on study treatment until repeat scans are obtained. Tumor flare may manifest as any factor causing radiographic progression per RECIST v1.1, including:

- Increase in the sum of diameters of target lesion(s) identified at baseline to ≥20% and ≥5 mm from nadir; Note: The iRECIST publication uses the terminology "sum of measurements," but "sum of diameters" will be used in this SAP, consistent with the original RECIST v1.1 terminology.
- Unequivocal progression of non-target lesion(s) identified at baseline; and
- Development of new lesion(s).

iRECIST defines new response categories, including unconfirmed PD (iUPD) and confirmed progressive disease (iCPD). For purposes of iRECIST assessment, the first visit showing progression according to RECIST v1.1 will be assigned a visit (overall) response of iUPD, regardless of which factors caused the progression.

At this visit, target and non-target lesions identified at baseline by RECIST v1.1 will be assessed as usual.

New lesions will be classified as measurable or non-measurable, using the same size thresholds and rules as for baseline lesion assessment in RECIST v1.1. From measurable new lesions, up to 5 lesions total (up to 2 per organ), may be selected as New Lesions — Target. The sum of diameters of these lesions will be calculated and kept distinct from the sum of diameters for target lesions at baseline. All other new lesions will be followed qualitatively as New Lesions — Nontarget.

Assessment at the Confirmatory Scans

On the confirmatory scans, the patient will be classified as progression confirmed (with an overall response of iCPD), or as showing persistent unconfirmed progression (with an overall response of iUPD), or as showing disease stability or response (stable disease [iSD]/partial response [iPR]/complete response [iCR]).

Confirmation of Progression

Progression is considered confirmed, and the overall response will be iCPD, if ANY of the following occurs:

- · Any of the factors that were the basis for the initial iUPD show worsening; or
 - For target lesions, worsening is a further increase in the sum of diameters of ≥5 mm, compared to any prior iUPD time point;
 - For non-target lesions, worsening is any significant growth in lesions overall, compared to a prior iUPD time point; this does not have to meet the "unequivocal" standard of RECIST v1.1; or
 - o For new lesions, worsening is any of these:
 - An increase in the new lesion sum of diameters by ≥5 mm from a prior iUPD time point;
 - Visible growth of new non-target lesions; or
 - The appearance of additional new lesions.
- Any new factor appears that would have triggered PD by RECIST v1.1.

Persistent iUPD

Progression is considered not confirmed, and the overall response remains iUPD, if:

None of the progression-confirming factors identified above occurs; AND

The target lesion sum of diameters (initial target lesions) remains above the initial PD threshold (by RECIST v1.1).

Additional scans for confirmation are to be scheduled 4 weeks to ≤8 weeks from the scans on which iUPD is seen. This may correspond to the next visit in the original visit schedule. The assessment of the subsequent confirmation scan will proceed in an identical manner, with possible outcomes of iCPD, iUPD, and iSD/iPR/iCR.

Resolution of iUPD

Progression is considered not confirmed, and the overall response becomes iSD/iPR/iCR, if:

None of the progression-confirming factors identified above occurs; AND

The target lesion sum of diameters (initial target lesions) is not above the initial PD threshold.

The response is classified as iSD or iPR (depending on the sum of diameters of the target lesions), or iCR if all lesions resolve.

In this case, the initial iUPD is considered to be pseudoprogression, and the level of suspicion for progression is "reset." This means that the next visit that shows radiographic progression, whenever it occurs, is again classified as iUPD by iRECIST, and the confirmation process is repeated before a response of iCPD can be assigned.

Management Following the Confirmatory Scan

If repeat scans do not confirm PD per iRECIST, as assessed by the Investigator, study intervention is to continue, and the regular scan schedule is to be followed. If PD is confirmed, patients may be discontinued from study intervention.

Note: If a patient has confirmed radiographic progression (iCPD), clinically meaningful study intervention may be continued after consultation with the Sponsor. In this case, if study treatment is continued, tumor imaging should continue to be performed.

Detection of Progression at Visits After Pseudoprogression Resolves

After resolution of pseudoprogression (ie, after iSD/iPR/iCR), another instance of progression (another iUPD) is indicated by any of the following events:

- Target lesions;
 - Sum of diameters reaches the PD threshold (≥20% and ≥5 mm increase from nadir) either for the first time, or after resolution of previous pseudoprogression. The nadir is always the smallest sum of diameters seen during the entire study, either before or after an instance of pseudoprogression.
- Non-target lesions; or
 - If non-target lesions have never shown unequivocal progression, their doing so for the first-time results in iUPD; or
 - If non-target lesions have shown previous unequivocal progression, and this
 progression has not resolved, iUPD results from any significant further growth of
 non-target lesions, taken as a whole.
- New lesions:
 - New lesions appear for the first time;
 - Additional new lesions appear;
 - Previously identified new target lesions show an increase of ≥5 mm in the new lesion sum of diameters, from the nadir value of that sum; or
 - o Previously identified non-target lesions show any significant growth.

If any of the events above occur, the overall response for that visit is iUPD, and the iUPD evaluation process (see Assessment at the Confirmatory Scans above) is repeated. Progression must be confirmed before iCPD can occur.

The decision process on the subsequent iUPD is identical to the iUPD confirmation process for the initial PD, with 1 exception, which could occur if new lesions had occurred at a prior instance of iUPD, had not resolved, then worsened (increase in size or number) leading to the second iUPD. If new lesion worsening has not resolved at the confirmatory scan, then iUPD cannot resolve to iSD or iPR. It will remain iUPD until either a decrease in the new lesion burden allows resolution to iSD or iPR, or until new or worsening causes of progression indicates iCPD.

Additional details about the iRECIST are provided in the iRECIST publication.

APPENDIX D: itRECIST GUIDANCE

Intratumoral-Response Evaluation Criteria in Solid Tumors (itRECIST) is based on the Response Evaluation Criteria in Solid Tumors (RECIST) version 1.1 and immune-RECIST but adapted to account for the unique tumor response seen with intra-tumoral immunotherapeutic drugs. itRECIST will be used by the Investigator to assess tumor response.

APPENDIX E: DATE OF IMPUTATION GUIDELINE

The following date imputation guidelines will apply to adverse events, prior medications and concomitant medications.

AE Start Date	AE Stop Date	Action
Known	Known/Partial/Missing	If start date < study drug start date, then not TEAE If start date ≥ study drug start date, then TEAE
Partial, but the known date components show that it cannot be on or after study drug start date	Known/Partial/Missing	Not TEAE
Partial, could be	Known	If stop date < study drug start date, then not TEAE
on or after study drug start date		If stop date ≥ study drug start date, then TEAE
	Partial	Impute stop date as latest possible date (ie, last day of month if day is unknown or 31-Dec if day and month are unknown), then:
		If stop date < study drug start date, then not TEAE
		If stop date ≥ study drug start date, then TEAE
	Missing	Assumed TEAE
Missing	Known	If stop date < study drug start date, then not TEAE
		If stop date ≥ study drug start date, then TEAE
	Partial	Impute stop date as latest possible date (ie, last day of month if day is unknown or 31st December if day and month are unknown), then:
		If stop date < study drug start date, then not TEAE
		If stop date ≥ study drug start date, then TEAE
	Missing	Assumed TEAE

CM Start Date	CM Stop Date	Action
Known	Known	If stop date < study drug start date, assign as PRIOR
		If stop date ≥ study drug start date, and start date ≤ end of treatment +30 days, assign as CONCOMITANT
		If stop date ≥ study drug start date and start date > 30 days after the end of treatment, assign as POSTTREATMENT
	Partial	Impute stop date as latest possible date (ie, last day of month if day unknown or 31-Dec if day and month are unknown), then:
		If stop date < study drug start date, assign as PRIOR
		If stop date ≥ study drug start date, and start date ≤ end of treatment +30 days, assign as CONCOMITANT
		If stop date ≥ study drug start date, and start date > 30 days after the end of treatment, assign as POSTTREATMENT
	Missing	If stop date is missing, then PRIOR will never be assumed or assigned
		If start date ≤ end of treatment, assign as CONCOMITANT
		If start date > 30 days after the end of treatment, assign as POSTTREATMENT
Partial	Known	Impute start date as earliest possible date (ie, first day of month if day unknown or 01-Jan if day and month unknown), then:
		If stop date < study drug start date, assign as PRIOR
		If stop date ≥ study drug start date and start date ≤ end of treatment + 30 days, assign as CONCOMITANT
		If stop date ≥ study drug start date and start date > 30 days after the end of treatment, assign as POSTTREATMENT
	Partial	Impute start date as earliest possible date (ie, first day of month if day unknown or 01-Jan if day and month are unknown) and impute stop date as latest possible date (ie, last day of month if day unknown or 31-Dec if day and month are unknown), then:
		If stop date < study drug start date, assign as PRIOR
		If stop date ≥ study drug start date and start date ≤ end ofe treatment + 30 days, assign as CONCOMITANT
		If stop date ≥ study drug start date and start date > 30 days after the end of treatment, assign as POSTTREATMENT

CM Start Date	CM Stop Date	Action
	Missing	Impute start date as earliest possible date (ie, first day of month if day unknown or 01 Jan if day and month unknown), then:
		If stop date is missing, then PRIOR will never be assumed or assigned
		If start date ≤ end of treatment + 30 days, assign as CONCOMITANT
		If start date > 30 days after the end of treatment, assign as POSTTREATMENT
Missing or Unknown	Known	If stop date < study drug start date, assign as PRIOR
		If stop date ≥ study drug start date, assign as CONCOMITANT
		If start date is missing, then POST-TREATMENT will never be assumed or assigned
	Partial	Impute stop date as latest possible date (ie, last day of month if day unknown or 31-Dec if day and month are unknown), then:
		If stop date < study drug start date, assign as PRIOR
		If stop date ≥ study drug start date, assign as CONCOMITANT
		If start date is missing, then POSTTREATMENT will never be assumed or assigned
	Missing	Assign as CONCOMITANT

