3.1.6 Handling of Dropouts and Missing Data

In general, missing data values will be recorded as missing and will not be imputed for the statistical analysis unless specified otherwise.

For missing or partial AEs and concomitant medications (CM) dates, conservative conventions will be applied in order to assign the events to corresponding periods (e.g. treatment period to ensure that no TEAE is missed). AEs will be considered as treatment-emergent, and the medications will be considered as concomitant if the missing/partial dates cannot definitively exclude the treatment period. Handling incomplete dates (e.g., AE and concomitant medications) are described in Appendix E.

Treatment duration

For the calculation of treatment duration, the date of last study drug infusion should be consistent with that of the last dose on the dosing page of the electronic case report form (eCRF). If the date of last dose on the dosing page is missing on the eCRF, use the last available dose date on the dosing page of eCRF to calculate. The last infusion should be clearly recorded on eCRF and not be estimated by the date of returning remaining study drug.

Laboratory values

Unless otherwise specified, for laboratory values that are reported using a non-numeric qualifier (e.g., less than [<] or greater than [>] sign), the reported numeric values will be used for summary or analysis without the qualifier.

In some cases, when the White Blood Cells (WBC) count is too low, the WBC differentials may be difficult to detect and thus not reported by the lab. If the reported WBC count < 0.5*10^9/L, then the differentials such as absolute neutrophils value will be imputed as zero for both the lab value summary and the Common Terminology Criteria for Adverse Events (CTCAE) v5.0 grading. For example, absolute neutrophils value imputed as 0 would be considered as grade 4.

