3.3.7 Prior & Concomitant Medications

All medications and therapies taken within 28 days prior to the Screening Visit until the Safety Follow-up Visit will be recorded in the eCRF. Prior medications include medications that were taken prior to and stopped before the first dose of the study treatment. Concomitant medications include medications that were taken on or after the first dose date of the study treatment until 30 days after the last dose of study treatment.

All prior and concomitant medications will be coded using the World Health Organization (WHO) Drug Dictionary (WHODrug Global B3, Version March 2022). Concomitant medications will be summarized by Anatomical Therapeutic Chemical (ATC) and preferred term in total for the Safety Analysis Set. For each medication, the ATC used in the summary is taken as the highest available level from among ATC1, ATC2, ATC3, and ATC4. That is, if ATC4 is available, it will be used as the ATC for the summary, but if not available then the next highest level will be used. Although a patient may have taken two or more medications, the patient is counted only once within each ATC and preferred term classification. The same patient may contribute to two or more preferred terms in the same ATC classification.

All prior and concomitant medication data will be listed by patient for the Safety Analysis Set.

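### SAP Appendix E leaves a concomitant medication with a known start 1 to 30 days after end of treatment and no stop date in no category, contradicting SAP Section 3.3.7

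*SAP*

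**What the plan says.** SAP Section 3.3.7 defines concomitant medications as those "taken on or after the first dose date of the study treatment until 30 days after the last dose of study treatment". They are summarised by ATC class and preferred term in the Safety Analysis Set, each patient counting once per class and term. The same section lists every prior and concomitant medication record by patient.

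SAP Section 3.1.6 passes incomplete dates on: "Handling incomplete dates (e.g., AE and concomitant medications) are described in Appendix E".

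In Appendix E, the medication row for a known start and a missing stop has three lines. The first rules out the prior category altogether. The second sets the limit for concomitant use: "If start date ≤ end of treatment, assign as CONCOMITANT". The third covers only starts later than day 30, which it calls post-treatment.

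The row for a partial start and a missing stop has the same first and third lines, but its concomitant line is "If start date ≤ end of treatment + 30 days, assign as CONCOMITANT". The rows with a known start and a known or partial stop also use the longer window: "start date ≤ end of treatment +30 days, assign as CONCOMITANT".

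**The concern.** The three lines for a known start and missing stop do not cover all possible start dates. The concomitant line ends at end of treatment and the post-treatment line starts after day 30, so the 30 days between belong to neither. Prior is ruled out as well. No other row that tests a start date has this gap, and the body text of the SAP puts those 30 days in the concomitant period.

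At stake is the concomitant-medication summary table. A drug begun shortly after treatment ended, with no stop date entered, could be missing from it. The trial means to collect these days: medications are recorded up to the Safety Follow-up Visit, which the protocol (Section 3.1.2) sets at 30 days after the last CyPep-1 injection. The report is also mainly a safety report, since SAP Section 1 promises full safety reporting and only selected efficacy endpoints.

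**Working it through.** The plan gives no figure to reproduce. The check is whether the lines of each row cover every start date once.

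**1. The rows that test a start date (SAP Appendix E).**

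| Start / stop | Latest start for concomitant | Post-treatment begins |
|---|---|---|
| Known / known | end of treatment + 30 days | after day 30 |
| Known / partial | end of treatment + 30 days | after day 30 |
| **Known / missing** | **end of treatment** | **after day 30** |
| Partial / known | end of treatment + 30 days | after day 30 |
| Partial / partial | end of treatment + 30 days | after day 30 |
| Partial / missing | end of treatment + 30 days | after day 30 |

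The three rows with a missing start date do not test it, so the question does not arise there.

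**2. The size of the gap.** Let d be the start date minus end of treatment, in days, and w the window in the concomitant line. The known/missing row assigns concomitant if d ≤ w and post-treatment if d > 30. For w ≤ 30, the unassigned start days are w + 1 to 30, which is 30 − w days.

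- As written, w = 0: days 1 to 30 are unassigned, 30 − 0 = 30 days.
- With 30 days added, w = 30: 30 − 30 = 0 days are unassigned, and none is assigned twice.

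Going through every start day from 200 days before to 120 days after end of treatment gives the same result: 30 unassigned days as written, none after the change, and no overlap in either case. The known/known row has no gap.

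**3. One drug, started 15 days after end of treatment.**

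- Known start, known stop: 15 ≤ 30, concomitant.
- Partial start, missing stop: the start is imputed to its earliest possible date, which cannot be later than day 15, so concomitant.
- Both dates missing: concomitant.
- Known start, missing stop: 15 > 0 and 15 is not above 30, so no category.

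A better-recorded start date gives the worse result. That points to a slip in one cell, not a choice. The row's own post-treatment line also presupposes the 30-day window.

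**4. Ceiling on the effect in the table.** Six patients are planned for Phase 1b (SAP Section 2.3.5). One patient is 1/6 = 16.7% of a row. A patient counts once per class and term, so the row changes only if that patient has no other qualifying record in it.

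**5. Where day 0 lies.** Appendix E does not define end of treatment, whereas Section 3.3.7 counts from the last dose. The figures above take the two as the same day. If end of treatment were read as the EoT Visit, set at 7 (±2) days after the last administration in protocol Section 4.5.3, day 0 would move 5 to 9 days later. The gap would still be 30 days long, of which 30 − 9 = 21 to 30 − 5 = 25 days would lie inside the Section 3.3.7 window.

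**The case against.** The strongest reply is that Section 3.3.7 already settles the matter. A drug with a known start on day 10 after the last dose meets that definition whatever its stop date, so nothing needs imputing. The programming specifications are a separate document (SAP Section 7) and may follow the definition. This stands against any claim that records will be lost. It does not remove the contradiction: Section 3.1.6 sends records with an incomplete date to Appendix E, and this row gives a different answer from the definition. The general convention in Section 3.1.6 does not clearly rescue it either. That convention treats a drug as concomitant when its dates cannot rule out the treatment period, and a known start after end of treatment does rule it out unless the period is read to include the following 30 days.

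A reader might infer more, and the documents do not support it:

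- **That these drugs certainly drop out, or that data are lost.** Omission from the table requires literal programming of this row. The by-patient listing keeps every record, and with about 6 patients it is easily read.
- **That missing stop dates are common because they mark ongoing drugs.** Neither document says how the eCRF records an ongoing medication. This is a plausible assumption, no more.
- **That the whole 30-day window is affected.** Collection stops at the Safety Follow-up Visit, which is timed from the last CyPep-1 injection and is skipped in some cases, so fewer days may be recorded.
- **That adverse events would no longer match their treatments.** The SAP plans no analysis linking the two. The 30-day TEAE limit stands in Section 3.7.1, while the Appendix E adverse-event rules have no upper limit, so the two sets of Appendix E rules differ anyway.

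**Conclusion.** The known-start, missing-stop row is wrong as written, at the lowest severity. It leaves 30 start days without a category and contradicts Section 3.3.7 and the five other rows that test a start date.

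The consequence is conditional. If the row is programmed literally, the affected records are left out of one descriptive table but stay in the listing. DLT, TEAE and efficacy results do not depend on it. The documents do not show how many records are affected, and it may be none. The figure of about 17 points is a one-patient ceiling, not an expected effect. It assumes the 6 planned patients and no other qualifying record for that patient in the row.

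**What to change.** In SAP Appendix E, replace the concomitant line in the known-start, missing-stop row with the wording already used for a partial start and missing stop: "If start date ≤ end of treatment + 30 days, assign as CONCOMITANT". Days 1 to 30 then become concomitant, day 31 onward stays post-treatment, and the row agrees with its neighbours and with Section 3.3.7.

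Also state in Appendix E that end of treatment means the last dose of either study drug, so that its window starts on the same day as the one in Section 3.3.7. Check that the separate programming specifications follow the corrected row.

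The cost is one phrase and one clarifying sentence in the SAP, and one line of code. There is no statistical downside.
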